11 ETHICS/PROTECTION OF HUMAN SUBJECTS.....20

11.1 Ethical Standard.....20

11.2 Laws and regulations.....20

11.3 Institutional Review Board.....20

11.4 Informed Consent Process.....21

11.5 Participant and data Confidentiality.....21

12 DATA HANDLING AND RECORD KEEPING.....21

12.1 Study Records Retention.....21

12.2 Protocol Deviations.....22

12.3 Publication and Data Sharing Policy.....22

13 CONFLICT OF INTEREST POLICY.....22

14 LITERATURE REFERENCES.....22

APPENDIX I: Schedule of events.....24

APPENDIX II: STATEMENT OF COMPLIANCE.....25

LIST OF ABBREVIATIONS

AE	Adverse Event
CFR	Code of Federal Regulations
CPT	Current Procedural Terminology
CRF	Case Report Form
FDA	Food and Product Administration
GCP	Good Clinical Practice
HIPAA	Health Insurance Portability and Accountability Act of 1996
ICD-10	International Classification of Disease, 10th Revision
ICF	Informed Consent Form
ICH	International Conference on Harmonisation
IRB	Institutional Review Board
PD	Pilonidal Disease
PI	Principal Investigator
PMS	Post-Market Surveillance
PQL	Postoperative Quality of Life Instrument
SAE	Serious Adverse Experience
SUB-I	Sub-Investigator

PROTOCOL SUMMARY

Title:	The Management of Pilonidal Wounds with ACell MicroMatrix® and Cytal® Wound Matrix: A Case Series.
Protocol Number:	CA2018-001
Study Design:	A case series involving the concomitant use of MicroMatrix® and Cytal™ Wound Matrix 2-Layer with standard of care negative pressure wound therapy (NPWT) during the management of pilonidal wound healing.
Objectives:	The purpose of this study is to examine the wound healing effect of MicroMatrix and Cytal Wound Matrix 2-Layer on pilonidal wound healing. All wounds will also receive standard of care negative pressure wound therapy. The study will measure the rate of wound closure within the 3 month time period. Patient reported outcomes as measured using the Visual Analog Pain Scale (VAS) and Katz Index of Independence in Activities of Daily Living (Katz ADL) will also be reported.
Number of Subjects:	A total of ten (10) subjects will be included in this series.
Study Criteria:	Inclusion Criteria: 
1. Subject has a clinical diagnosis of pilonidal disease.2. Subject is being scheduled for surgical excision of pilonidal disease.3. Subject is at least 18 years of age.4. Subject is willing and able to adhere to protocol requirements and agrees to participate in the study program and comply with the study follow-up regimen.5. Subject is willing to provide written informed consent. Exclusion Criteria: 
1. Subject has a known allergy to porcine-based materials.2. Subject is pregnant.
Number of Sites:	One

Site Locations:

Florida Hospital Tampa
[name]
[name]

Southeastern Center for Digestive Disorders and Pancreatic
Cancer
[name]
[name]

Study Product(s):

1. MicroMatrix®
2. Cytal™ Wound Matrix 2-Layer

**Participant & Study
Duration:**

This study has an estimated overall duration of 6-8 months.
Individual subject participation will be approximately 3 months..

Statistical Methodology:

Wound area will be analyzed for size and percentage closure during specified subject follow up period. The mean, median and standard deviations will be calculated and scatter plots developed to determine healing rates by application number, and days in treatment. The mean number of application of product will be tabulated.

Safety will be assessed during the course of the study by collection of AEs as outlined in the Schedule of Events. All summaries of AEs will be based on treatment-emergent AEs and presented using the incidence and a tabulation of the number of events. The number and percentage of subjects experiencing AEs will be summarized by system organ class and description. Summaries by maximum severity and relationship to the study treatment will also be provided. SAEs and AEs leading to discontinuation from the study will be presented by system organ class and preferred term.

Baseline demographic factors, patient characteristics and concomitant medications will be summarized. This summary will include the gender, age in years at the time of entry into the study, race, ethnicity, height (inches), weight (pounds) and BMI. Age, height, weight, and BMI will be summarized using descriptive statistics. The number and percent of each gender, race, and ethnicity category will be presented using counts and percentages.

The medical and surgical history will be coded for each patient and summarized based on the body system description. The

patients will be summarized using counts and percentages for those patients who had a pre-study medical history.

Patient reported outcomes as measured using the Visual Analog Pain Scale (VAS) and Katz Index of Independence in Activities of Daily Living (Katz ADL) will be summarized.

2 INTRODUCTION: BACKGROUND INFORMATION AND SCIENTIFIC RATIONALE

2.1 BACKGROUND INFORMATION

Pilonidal disease is an inflammatory process affecting the skin and subcutaneous tissue of the lower back and intergluteal fold. The pathophysiology of pilonidal disease is not entirely clear. Pilonidal disease was originally believed to be congenital, secondary to abnormal skin in the gluteal cleft. However, the current widely accepted theory describes pilonidal disease as an acquired condition related to the presence of hair in the natal cleft skin; loose hairs create a foreign body reaction that leads to formation of midline pits, then secondary infection. Pilonidal disease typically presents in the second decade of life, and affects men three to four times more often than women. It is a common problem encountered by surgeons, with an incidence estimated at 26 patients per 100,000 people. In the United States alone, pilonidal disease is estimated to affect 70,000 patients annually. The disease creates a significant burden, as treatment costs entail not only the surgical procedure and hospital stay, but postoperative wound care and loss of earnings due to time taken off and chronicity of disease.

2.2 RATIONALE

Pilonidal disease is a chronic disease with a major impact on patient quality of life and productivity. Thus, improved wound healing would have a significant effect on patient quality outcomes, patient quality of life, and healthcare utilization, as well as societal benefits from allowing this vital population to return to productivity. There is no consensus on postoperative wound care after surgery for pilonidal disease. Negative pressure therapy is commonly used. However, this therapy is costly and cumbersome, and not evidence-based to optimize wound healing or postoperative patient or financial outcomes. Our goal is to examine the effect of the concomitant use of MicroMatrix[®] and Cytal[™] Wound Matrix 2-Layer on pilonidal wound healing when used in combination with NPWT.

Our premise is that Cytal[™] Wound Matrix 2-Layer and MicroMatrix[®] will demonstrate a positive trend on healing outcomes.

3 OBJECTIVES AND PURPOSE

Primary objective:

The purpose of this study is to examine the wound healing effect of MicroMatrix and Cytal Wound Matrix 2-Layer on pilonidal wounds. All wounds will also receive standard of care negative pressure wound therapy. The study will measure the rate of wound closure within the 3 month time period. Patient reported outcomes as measured using the Visual Analog Scale (VAS) and Katz Index of Independence in Activities of Daily Living (Katz ADL) will also be reported.

4 STUDY DESIGN

4.1 DESCRIPTION OF THE STUDY DESIGN

A prospective case series examining the concomitant use of MicroMatrix® and Cytal™ Wound Matrix 2-Layer with standard of care negative pressure wound therapy (NPWT) during the management of pilonidal wound healing. Wound healing will be evaluated at 2 weeks, 6 weeks and 3 months. If subjects heal prior to the 3 month visit, wound healing shall be documented at the visit.

A maximum of ten (10) subjects will be included in this series.

This study has an estimated overall duration of 6-8 months. Individual subject participation will be approximately 3 months.

5 STUDY ENROLLMENT AND WITHDRAWAL

5.1 PARTICIPANT INCLUSION CRITERIA

In order to be eligible to participate in this study, an individual must meet all of the following criteria:

Inclusion Criteria:

1. Subject has a clinical diagnosis of pilonidal disease.
2. Subject is being scheduled for surgical excision of pilonidal disease.
3. Subject is at least 18 years of age.
4. Subject is willing and able to adhere to protocol requirements and agrees to participate in the study program and comply with the study follow-up regimen.
5. Subject is willing to provide informed consent.

5.2 PARTICIPANT EXCLUSION CRITERIA

An individual who meets any of the following criteria will be excluded from participation in this study:

Exclusion Criteria:

1. Subject has a known allergy to porcine-based materials.
2. Subject is pregnant.

5.3 STRATEGIES FOR RECRUITMENT AND RETENTION

Subjects will be recruited from the medical offices of the Principal Investigator, [name], and Co-Investigator, [name]. A maximum of 10 subjects will be included in this series.

5.4 PARTICIPANT WITHDRAWAL OR TERMINATION

5.4.1 REASONS FOR WITHDRAWAL OR TERMINATION

A subject may be discontinued from the study at any time if the subject, the Investigator, or the Sponsor feels that it is not in the subject's best interest to continue. The following is a list of *possible* reasons for study treatment discontinuation:

1. Screen failure
2. Subject withdrawal of consent (or assent)
3. Subject is not compliant with study procedures
4. Adverse event that in the opinion of the Investigator would be in the best interest of the subject to discontinue study participation
5. Protocol violation requiring discontinuation
6. Lost to follow-up
7. Sponsor request for early termination of study
8. Subject death

All subjects are free to withdraw from participation at any time, for any reason, specified or unspecified, and without prejudice.

Reasonable attempts will be made by the Investigator to provide a reason for subject withdrawals. The reason for the subject's withdrawal from the study will be specified in the subject's source documents.

The Investigator must make every effort to contact subjects who are lost to follow-up. Attempts to contact such subjects must be documented in the patients' records (e.g., times and dates of at least 3 attempts via telephone/email, receipt for sending a registered letter).

If a subject is withdrawn from treatment due to an Adverse Event, the subject will be followed and treated by the Investigator until the abnormal parameter or symptom has resolved or stabilized.

5.4.2 HANDLING OF PARTICIPANT WITHDRAWALS OR TERMINATION

Although subjects may withdraw from the study at any time and for any reason (or may be withdrawn at the Investigator's discretion), subject withdrawal should be avoided as much as reasonably possible.

Subjects who prematurely discontinue are not to be replaced. For subjects considered lost to follow-up, the data collection forms must be completed up to the last visit performed.

5.5 PREMATURE TERMINATION OR SUSPENSION OF STUDY

This study may be temporarily suspended or prematurely terminated if there is sufficient reasonable cause. Written notification, documenting the reason for study suspension or termination, will be provided by the suspending or terminating party to the Investigator, Sponsor and Institutional Review Board (IRB), as appropriate. If the study is prematurely terminated or suspended, the PI will promptly inform the IRB and will provide the reason(s) for the termination or suspension.

Circumstances that may warrant termination or suspension include, but are not limited to:

- * Determination of unexpected, significant, or unacceptable risk to participants
- * Demonstration of efficacy that would warrant stopping
- * Insufficient compliance to protocol requirements
- * Data that are not sufficiently complete and/or evaluable
- * Determination of futility

Study may resume once concerns about safety, protocol compliance, data quality are addressed and satisfy the Sponsor and/or IRB.

6 STUDY DEVICE

6.1 STUDY DEVICE DESCRIPTION

6.1.1 DEVICE DESCRIPTION

MicroMatrix®

MicroMatrix® is composed of a porcine-derived extracellular matrix known as urinary bladder matrix and is intended for the management of wounds including: partial and full-thickness wounds, pressure ulcers, venous ulcers, diabetic ulcers, chronic vascular ulcers, tunneled/undermined wounds, surgical wounds (donor sites/grafts, post-Mohs surgery, post-laser surgery, podiatric, wound dehiscence), trauma wounds (abrasions, lacerations, second-degree burns, skin tears) and draining wounds. The device is intended for one-time use.

Cytal™ Wound Matrix 2-Layer

Cytal™ Wound Matrix 2-Layer is composed of a porcine-derived extracellular matrix also known as urinary bladder matrix. The device is intended for the management of wounds including: partial and full-thickness wounds, pressure ulcers, venous ulcers, diabetic ulcers, chronic vascular ulcers, tunneled/undermined wounds, surgical wounds (donor sites/grafts, post-Mohs surgery, post-laser surgery, podiatric, wound dehiscence), trauma wounds (abrasions, lacerations, second-degree burns, skin tears) and draining wounds. The device is intended for one time use.

Negative Pressure Wound Therapy

The V.A.C.Via™ Negative Pressure Wound Therapy System is an integrated wound management system for use in acute, extended and home care settings. It is intended to create an environment that promotes wound healing by secondary or tertiary (delayed primary) intention by preparing the wound bed for closure, reducing edema, promoting granulation tissue formation and perfusion, and by removing exudates and infectious material. It is indicated for patients with chronic, acute, traumatic, subacute and dehisced wounds, partial-thickness burns, ulcers (such as diabetic, pressure or venous insufficiency), flaps and grafts.

6.1.2 ACQUISITION

MicroMatrix® and Cytal™ Wound Matrix 2-Layer are commercially available and will be obtained through ACell distribution methods.

6.1.3 STUDY DEVICE STORAGE

MicroMatrix® and Cytal™ Wound Matrix 2-Layer should be stored in a clean, dry environment at room temperature in the unopened and undamaged package. The products should be protected from freezing, excessive heat, and high humidity.

6.2 POTENTIAL RISKS AND BENEFITS

6.2.1 POTENTIAL RISK AND PRODUCT WARNINGS

MicroMatrix® and Cytal® Wound Matrix 2-Layer

Complications and reactions are possible with any soft tissue repair, including but not limited to:

- * infection
- * increased chronic inflammation
- * allergic reaction
- * unexplained fever or chills
- * excessive redness
- * pain
- * swelling

- * odor associated with the use of products during the healing phase
- * excessive drainage from the wound

Negative Pressure Wound Therapy

NPWT is contraindicated on the following situations:

- * exposed organs, blood vessels, vascular grafts, or unexplored enteric fistulas
- * active, untreated infection
- * necrotic tissue
- * malignancy tissue (within the wound)
- * fragile skin
- * active hemorrhage / coagulopathy / anticoagulation
- * adhesive allergy

6.2.2 POTENTIAL BENEFITS

Benefits of study participation are unknown. This study may or may not directly benefit participants. However, the study may provide information that will benefit future patients.

7 STUDY PROCEDURES AND SCHEDULE

7.1 STUDY PROCEDURES/EVALUATIONS

7.1.1 STUDY SCHEDULE

A Schedule of Events representing the required testing procedures to be performed for the duration of the study is diagrammed in Appendix I. All follow-up visits will occur relative to the Treatment Visit, as outlined below:

7.1.2 BASELINE VISIT

The baseline visit may occur up to 5 days prior to the Treatment Visit.

1. Obtain informed consent of potential participant (or legally authorized individual).
2. Assign subject identification number (SID). SIDs will be assigned in consecutive order and not be re-used in the case of Screen Failures.
3. Obtain demographic information, medical history, height, weight and prior pilonidal wound procedures
4. Review medical history to determine eligibility based on inclusion/exclusion criteria.
5. Verify pregnancy test results if applicable
6. Obtain Subject Quality of Life Assessments (Visual Analogue Scale (VAS), Katz Index of Independence in Activities of Daily Living (Katz ADL))
7. Record each medication the subject is taking on the medication log.

7.1.3 TREATMENT VISIT

After all inclusion/exclusion criteria have been met, the patient becomes eligible for enrollment.

1. Confirm inclusion/exclusion criteria
2. Record procedure date, name of surgeon
3. Record surgical details (indication for surgery, procedure performed)
4. Obtain post-excisional images of wound area
5. Record wound measurements
6. Treat wound using Cytal[®] 2-layer and MicroMatrix[®]. Record study device details as required.

7.1.4 FOLLOW-UP VISITS (2 WEEKS \pm 7 DAYS; 6 WEEKS \pm 7 DAYS; 3 MONTHS \pm 1 MONTH)

1. Obtain wound photograph and size measurements.
2. Perform wound assessment.
3. Record changes in medication.
4. Determine recurrence and necessitation for reoperation.
5. If wound requires retreatment with Cytal[®] 2-layer and MicroMatrix[®] record device application information
6. Obtain Visual Analogue Scale (VAS), Katz Index of Independence in Activities of Daily Living (Katz ADL))
7. Record any pilonidal wound related adverse events or serious adverse events.

7.1.5 UNSCHEDULED VISIT

Unscheduled visits may occur at any time after the treatment visit until the final study visit occurs. At an unscheduled visit, the patient will have their wound assessed and be evaluated for adverse events. The wound will also be photographed, measured, and documented

8 ASSESSMENT OF SAFETY

8.1 SPECIFICATION OF SAFETY PARAMETERS

8.1.1 DEFINITION OF ADVERSE EVENTS (AE)

Adverse event means any untoward medical occurrence associated with the use of an intervention in humans, whether or not considered intervention-related (21 CFR 312.32 (a)). Pilonidal wound related adverse events that occur post-treatment will be documented and evaluated under this protocol.

A pilonidal wound related medical condition that is present when the subject enters the study is not considered an AE unless the pilonidal wound related medical condition recurs after the subject had recovered from the pre-existing condition, or in the opinion of the Investigator, there is a clinically significant exacerbation in intensity or frequency during the study. If clinically significant worsening of the subjects' physical condition from screening is noted, the changes

will be documented as an AE. Clinical significance is defined as any pilonidal wound related variation in signs, symptoms, or testing that has medical relevance and may result in an alteration in medical care.

All disease signs and symptoms experienced by the subject and related to the pilonidal disease and wound will be recorded on the Adverse Event Form from the time of the index procedure until study completion. During each visit, each subject will be asked "Since your last clinic visit, have you had any new pilonidal wound related medical problems or any pilonidal wound related medical problems that have worsened since your last visit?" The Investigator/authorized designee shall record all directly observed pilonidal wound related AEs, all pilonidal wound related AEs as a response to the open question to the subject, and all pilonidal wound related AEs spontaneously reported by the subject during the study. Subjects will be told to notify their physician if they suspect they are experiencing an AE outside of the visit windows. All pilonidal wound related AEs shall be recorded and described in detail, recording the diagnosis, onset date, treatment, and resolution date. If the event is not resolved, a resolution date shall not be recorded and the event shall be recorded as "ongoing".

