8.3 TIME PERIOD AND FREQUENCY FOR EVENT ASSESSMENT AND FOLLOW-UP

The occurrence of an AE or SAE may come to the attention of study personnel during study visits or upon review by a study monitor. All AEs (per Investigator discretion) that are

possibly impactful to the development or healing of a pilonidal wound will be captured on the appropriate data collection form. Information to be collected includes event description, time of onset, clinician's assessment of severity, relationship to study device (assessed only by those with the training and authority to make a diagnosis), and time of resolution/stabilization of the event. All AEs will be followed to adequate resolution.

Any medical condition that is present at the time that the participant is screened will be considered as baseline and not reported as an AE. However, if the study participant's condition deteriorates at any time during the study, it will be recorded as an AE. UADEs will be recorded throughout the study.

Changes in the severity of an AE will be documented to allow an assessment of the duration of the event at each level of severity to be performed. AEs characterized as intermittent require documentation of onset and duration of each episode.

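### Adverse event recording is limited to undefined wound-related events in 8.1.1 and 7.1.4, filtered differently in 8.3, and tabulated in 9.1 with no stated limit

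*Combined protocol and SAP*

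**What the plan says.** Section 8.1.1 opens with a general definition: an AE is any untoward occurrence, whether or not it is thought to be related to the intervention. It then sets a narrower rule for what is recorded: "Pilonidal wound related adverse events that occur post-treatment will be documented and evaluated under this protocol". At each visit the subject is asked: "have you had any new pilonidal wound related medical problems or any pilonidal wound related medical problems that have worsened since your last visit". Events the Investigator observes directly are recorded under the same limit, and so are "all pilonidal wound related AEs spontaneously reported by the subject during the study". Clinical significance, which decides whether worsening since screening counts as an AE, is also defined as wound related. One sentence in 8.1.1 has no limit: "Subjects will be told to notify their physician if they suspect they are experiencing an AE outside of the visit windows".

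Item 7 of 7.1.4 (follow-up visits) reads: "Record any pilonidal wound related adverse events or serious adverse events".

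Section 8.3 uses another test. It covers AEs that are, at the Investigator's discretion, "possibly impactful to the development or healing of a pilonidal wound will be captured on the appropriate data collection form". After treating conditions present at screening as baseline, it adds that if the participant's "condition deteriorates at any time during the study, it will be recorded as an AE".

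Sections 7.1.5 and 8.4.1 and the AE row of Appendix I refer to adverse events with no qualifier.

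Section 9.1, repeated in the Protocol Summary, says AEs are collected as the Schedule of Events sets out. It summarizes treatment-emergent AEs by system organ class, maximum severity and relationship to treatment. Neither place says that only wound-related events were collected.

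**The concern.** A table of treatment-emergent AEs by system organ class is normally read as all-cause. Here the collection rule behind it is narrower, and it is not the same rule in every section. A reader of the 9.1 tables cannot tell whether they hold all AEs, wound-related AEs, or a mixture that depends on how each event came to notice. If the tables show no allergic reaction and no fever, three explanations remain open: none occurred, nobody asked, or the event was not counted as wound related.

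This matters because 6.2.1 itself lists allergic reaction and unexplained fever or chills among the possible complications, and these need not appear at the wound. Both products are porcine-derived (6.1.1), and known porcine allergy is an exclusion (5.2), so reactions of this kind are foreseen by the plan.

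**Working it through.** The plan gives no AE rate or capture rate, so there is no figure to reproduce. The check is a comparison of the sections, followed by three simple counts.

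**1. Scope by section**

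| Section | What it governs | Scope as worded |
|---|---|---|
| 8.1.1, definition | What an AE is | No wound limit |
| 8.1.1, recording rule | Observed, elicited and spontaneous reports | Wound related |
| 8.1.1, visit question | The only scripted prompt | Wound related |
| 7.1.4 item 7 | Scheduled follow-up visits | Wound related for AEs; unclear for serious AEs |
| 8.3, capture rule | Entry on the form | Possible effect on wound development or healing, at discretion |
| 8.3, deterioration | Worsening on study | No limit stated; may cover only conditions present at screening |
| 7.1.5, 8.4.1, Appendix I | Unscheduled visits, reporting, schedule | None stated; may or may not inherit 8.1.1 |
| 8.1.2, 8.4.2, 8.4.3, and the device-effect sentence in 8.3 | Serious events and unanticipated device effects | No wound limit |
| 9.1, Protocol Summary | Tables | Treatment-emergent; no wound limit stated |

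**2. Are the two explicit filters the same?** No. Relation to the wound concerns where an event comes from. The 8.3 test concerns what the event might do to healing. An event can arise from the wound without affecting healing, or affect healing without arising from the wound.

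**3. Following one event through the rules.** Take, as an illustration, a non-serious allergic reaction away from the wound between the 2-week and 6-week visits.
- The 6-week question does not ask about it.
- If the subject mentions it anyway, 8.1.1 records it only if the Investigator regards it as wound related.
- 8.3 records it only if the Investigator thinks it might affect healing.
- 8.4.1 records it if AE there has the general meaning, and not if it inherits the 8.1.1 limit.
- Item 3 of 7.1.4 ("Record changes in medication") could reveal it indirectly, but only if a medication was changed.
- If it is not recorded, it is not graded for device relationship, because 8.2.2 grades only AEs that have been collected. It is then absent from the 9.1 tables.

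**4. Counts**
- The phrase *pilonidal wound related* occurs 10 times in 8.1.1 and once in 7.1.4: 10 + 1 = 11. It is not defined in the document as supplied.
- Scheduled follow-up visits at which the restricted question is the only scripted prompt: 3 (2 weeks, 6 weeks, 3 months). At most 3 × 10 subjects = 30 subject-visits.
- Effect of one subject's classification on a tabulated percentage: 1/10 = 10 percentage points with 10 subjects.

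The last two counts describe exposure and sensitivity. They do not estimate how many events are lost.

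**The case against.** The strongest reply is that 8.1.1 is the definitions section and says which AEs this protocol documents, so later uses of AE carry its limit. On that view 8.4.1 governs only the timing of documentation and follow-up, 7.1.5 and the Appendix I row are shorthand, and the sentence on notifying a physician tells subjects whom to contact. This has force. A reader might infer that these places form a firm third scope in direct conflict with 8.1.1, but the text does not establish that. It does not establish inheritance either: the sentence that defines an AE is unrestricted, the wound limit is a recording rule added after it, and 8.3 supplies its own different filter. No section says which rule prevails. The layout of the Appendix I table may also have been damaged in extraction, so little should rest on it.

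Second, the restriction is deliberate-looking and repeated, in a descriptive series of commercially available products with no safety hypothesis. That is fair, and it is why a consistent, labelled restriction is an acceptable fallback. It does not explain the second filter in 8.3 or the unlabelled tables in 9.1.

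Third, an Investigator could readily treat an allergic reaction or fever as wound related, since the products are placed in the wound. That is possible. With the term undefined, the plan neither requires nor excludes it.

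Fourth, serious reactions are covered elsewhere. This stands. A reader might infer that serious reactions would also be missed, but the serious AE and unanticipated device effect rules carry no wound limit. The one loose end is item 7 of 7.1.4, which can be read as limiting serious events too.

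**Conclusion.** The point holds as an inconsistency in AE scope that leaves non-serious reactions away from the wound exposed: possibly unasked about, recorded inconsistently, and never graded for device relationship. Confidence is high on the wording. The loss of any actual event is a possibility and has not been shown.

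Its size cannot be given as a number of missed events, because the documents state no incidence or capture rate. It would go too far to say that the AE percentages will be understated by some amount, or that reactions will be missed. What can be said is that the restricted question is the only scripted prompt at up to 30 subject-visits, and that one subject counted differently moves a percentage by 10 points if 10 subjects are enrolled. The wound-area endpoint is not affected.

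The conclusion assumes that the AE form, which is not among the documents, does not itself settle the scope, and that no definition of the term stands in the pages that were removed. It should be fixed because it governs how the safety tables can be read. It does not prevent the study from being run.

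**What to change.** Reconcile 7.1.4, 8.1.1, 8.3 and 8.4.1 to one collection scope, and make 7.1.5 and Appendix I consistent with it. In item 7 of 7.1.4, make clear that serious events are recorded whether or not they are wound related.

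*Preferred.* Record all AEs from index treatment to last visit and remove the wound limit from the visit question. Add a wound-related yes/no field to the AE form, if it has none, next to device relationship. In 9.1 and the Protocol Summary, tabulate all treatment-emergent AEs, then the wound-related and device-related subsets.

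*If the restriction is deliberate.* Define wound related, use that one filter in every section, title the 9.1 tables as wound-related AEs only, and confine the safety conclusion to that scope.

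*Cost.* Both routes need a protocol amendment with IRB approval (11.3). The preferred route adds at most one form field and a few unrelated events to record, in at most 10 subjects over about 3 months each. The fallback adds no data collection, but non-serious reactions away from the wound remain unasked about.
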